The principal investigator is responsible for monitoring the data, assuring protocol compliance, and conducting the safety reviews at the specified frequency on a monthly basis. During the review process the principal investigator will evaluate whether the study should continue unchanged, require modification/amendment, or close to enrollment.

The principal investigator or the Institutional Review Board (IRB) have the authority to stop or suspend the study or require modifications.

This protocol presents minimal risks to the subjects and adverse events or other problems are not anticipated. In the unlikely event that such events occur, Reportable Adverse Events (which are events that are serious or life-threatening and unanticipated (or anticipated but occurring with a greater frequency than expected) and possibly, probably, or definitely related) or unanticipated problems involving risks to subjects or others will be reported in writing within 48 hours to

the IRB (using the appropriate forms from the website) and any appropriate funding and regulatory agencies. The investigator will apprise fellow investigators and study personnel of all adverse events that occur during the conduct of this research project through regular study meetings.

- d. For multi-site studies for which the Yale PI serves as the lead investigator:
- i. How will adverse events and unanticipated problems involving risks to subjects or others be reported, reviewed and managed?
 - ii. What provisions are in place for management of interim results?
 - iii. What will the multi-site process be for protocol modifications?

12. **Statistical Considerations:** Describe the statistical analyses that support the study design.
13.

Primary Outcome:

Incidence of delirium per admission of medical geriatric patients

Incidence of delirium per patient days of hospitalization in medical admission of geriatric patients

Secondary outcomes:

Risk factors associated with incident delirium

Duration of delirium by study group

Hospital length of stay

Sample size based was estimated using openepi.com (similar results with Stata version 14 sample size calculator) based on control group incidence of delirium in medical subgroup of 30%. (Chen et al: Exogenous melatonin for delirium prevention: a meta-analysis of randomized controlled trials - Molecular Neurobiology online publication 21 July 2015) with relative risk reduction of 30 %.

Sample Size: X-Sectional, Cohort, & Randomized Clinical Trials

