Two-sided significance level(1-alpha):	95
Power(1-beta, % chance of detecting):	80
Ratio of sample size, Unexposed/Exposed:	1
Percent of Unexposed with Outcome:	30
Percent of Exposed with Outcome:	21
Risk/Prevalence Ratio:	0.7
Risk/Prevalence difference:	-9

Sample size estimation by the Fleiss method yielded a total sample size of 734 with 367 in each group.

Descriptive statistics such as percentages for binary categorical variables, means and standard deviations for continuous variables. Fisher's exact test or chi-square test will be used to compare categorical variables. For continuous variables we will use t-test of unequal variances for means for normally distributed variables and the Wilcoxon-Mann-Whitney where normal distribution cannot be assumed. Risk ratio will be calculated using Stata statistical program version 14. (StataCorp LP, [name]) Associations with covariates will be tested using logistic regression with presence of incident delirium as the dependent variable.

Person days to delirium will be compared between the two groups using Survival analysis with Kaplan Meier curves, logrank test and Cox proportional hazards (covariates include age, comorbidities, medication numbers, presence of risk factors for delirium – polypharmacy, use of psychotropic or sedating medications, and use of bladder catheters).

Upon completing enrollment and analysis of 367 subjects, [name], a independent statistical expert, will analyze the data. In addition, an independent geriatrician expert in delirium will review any equivocal CAM results and make a decision as to the occurrence of delirium.

SECTION VI: RESEARCH INVOLVING DRUGS, BIOLOGICS, RADIOTRACERS, PLACEBOS AND DEVICES

If this section (or one of its parts, A or B) is not applicable, state N/A and delete the rest of the section.

A. DRUGS, BIOLOGICS and RADIOTRACERS

1. **Identification of Drug, Biologic or Radiotracer:** What is (are) the **name(s)** of the drug(s) biologic(s) or radiotracer(s) being used? Identify whether FDA approval has been granted and for what indication(s).

Melatonin—FDA categorized as a dietary supplement for sleep aid

All protocols which utilize a drug, biologic or radiotracer **not** approved by, but regulated by, the FDA, or a radiotracer regulated by the RDRC, must provide the following information:

a. What is the Investigational New Drug (IND) **number** assigned by the FDA?

FDA IND 129224-Melatonin

b. Who holds the IND?

[name]

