Yes If yes, describe the conditions under which continued access to study drug(s) may apply as well as conditions for termination of such access.

No If no, explain why this is acceptable.

SECTION VII: RECRUITMENT/CONSENT AND ASSENT PROCEDURES

1. Targeted Enrollment: Give the number of subjects:

- a. targeted for enrollment at Yale for this protocol: 734
(367 patients in the treatment and 367 patients in the placebo group)

2. Indicate recruitment methods below. Attach copies of any recruitment materials that will be used.

Flyers

Internet/Web Postings

Radio

- | | | |
|---|---|-------------------------------------|
|  Posters |  Mass E-mail Solicitation |  Telephone |
|  Letter |  Departmental/Center Website |  Television |
|  Medical Record Review |  Departmental/Center Research Boards |  Newspaper |
|  Departmental/Center Newsletters |  Web-Based Clinical Trial Registries | |
|  YCCI Recruitment database |  Clinicaltrials.gov Registry (do not send materials to HIC) | |
|  Other (describe): subjects that meet inclusion criteria will be approached by a member of the research team upon admission to the hospital and recruited for the study. | | |

3. Recruitment Procedures:

- a. Describe how potential subjects will be identified.

Utilizing OnCore and it's EPIC Support Team, a member of the research team will screen the list of admitted patients to the participating services daily to identify all new admissions who are appropriate candidates to enter the study. The electronic chart will then be reviewed to determine if the potential subjects meet all eligibility criteria and if concern for discharge within 48 hours is an issue then the primary treating team will be approached for their prediction/plan.

- b. Describe how potential subjects are contacted.

They will be approached on the medicine floor to which they are admitted by a member of the research team Within 24 hours of admission.

- c. Who is recruiting potential subjects?

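### Section V.12 lists two primary outcomes where Section V.3 and the sample size have one, gives no alpha rule, and sets the independent analysis at 367 subjects when the target is 734

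*Combined protocol and SAP*

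**What the plan says.** **Primary outcome.** Section V.3 (Research Plan) names one primary endpoint: whether Short CAM delirium occurs by discharge or before hospital day 15. Section V.12 (Statistical Considerations) lists two items under its primary outcome heading: "Incidence of delirium per admission of medical geriatric patients" and "Incidence of delirium per patient days of hospitalization in medical admission of geriatric patients". The sample size in V.12 is built on proportions of 30% and 21%, so it covers the first item only.

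**Tests.** V.12 states that Fisher's "exact test or chi-square test will be used to compare categorical variables", and that "Person days to delirium will be compared between the two groups using Survival analysis", with the log-rank test and Cox regression. It gives no order of testing, no rule on whether one or both outcomes must succeed, and no division of the 5% level.

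**Number at analysis.** The V.12 calculation "yielded a total sample size of 734 with 367 in each group". Section VII.1 repeats the figure: "targeted for enrollment at Yale for this protocol: 734" ("367 patients in the treatment and 367 patients in the placebo group"). The closing paragraph of V.12 then has an independent statistical expert analyse the data "Upon completing enrollment and analysis of 367 subjects". It does not say whether this is the final analysis, an interim look, or the per-group number written in place of the total.

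**The concern.** A confirmatory test at two-sided 5% needs one rule for success and one stated time of analysis. On the outcome, the plan does not say what follows if one primary outcome gives p<0.05 and the other does not. The two can differ, because one counts patients and the other takes account of time at risk. On timing, 367 is both the per-group number and exactly half of 734, so the sentence can be read in three ways with different consequences for power and error rate. If neither point is settled before results are known, a choice made afterwards could not be told apart from a planned one.

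**Working it through.** **Inputs from V.12:** control 30%, melatonin 21%, two-sided 5%, power 80%. Allocation is 1:1 (V.3 and V.12). The correlation between the two outcomes is not in the documents and is assumed below.

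**1. The plan's own figure.** Fleiss formula without continuity correction, mean proportion 0.255:

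n = [1.960 × √(2 × 0.255 × 0.745) + 0.842 × √(0.30 × 0.70 + 0.21 × 0.79)]² / 0.09²
= [1.960 × 0.6164 + 0.842 × 0.6131]² / 0.0081 = 366.99

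This rounds up to 367 per group, 734 in total. The stated sample size reproduces exactly and is not in dispute.

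**2. Power if 367 in total were the only analysis** (183.5 per group):

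z = [0.09 × √183.5 − 1.960 × 0.6164] / 0.6131 = (1.2192 − 1.2081) / 0.6131 = 0.018, so power is 50.7%.

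The same formula at 367 per group gives z = 0.842 and power 80.0%.

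**3. Two primary outcomes, one analysis, success on either.** False-positive rate = 1 − P(|Z₁| < 1.96 and |Z₂| < 1.96), bivariate normal with correlation ρ:

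| ρ (assumed) | False-positive rate |
|---|---|
| 0.98 | 5.9% |
| 0.95 | 6.5% |
| 0.90 | 7.0% |
| 0.87 | 7.3% |
| 0 | 1 − 0.95² = 9.75% |

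The range 0.87 to 0.98 comes from null simulations of the chi-square test against the unadjusted log-rank test. They used 367 per group, 30% delirium, gamma-distributed stays with mean 4, 6 or 8 days capped at 14 days, a constant or falling hazard, and half-day assessments. Apart from the group size, the 30%, the 14-day limit and the twice-daily assessments, these settings are assumptions. The range is not a bound, and the covariate-adjusted Cox model was not simulated. The independent case is shown as an outer figure. It is unlikely, since both outcomes count the same event.

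**4. Per admission alone decides, or a fixed sequence, with one analysis.** The false-positive rate is 5.0%, N is 734 and power is 80%.

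**5. An unadjusted by-arm look at 367 and again at 734, one outcome.** The correlation between looks is √(367/734) = 0.707. If |Z| > 1.96 at either look counts as success, the rate is 8.3%.

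**6. Cost of splitting alpha instead (2.5% each, critical value 2.241).** Power for per admission at 734: z = (0.09 × √367 − 2.241 × 0.6164) / 0.6131 = 0.559, so 71.2%. Restoring 80% needs [2.241 × 0.6164 + 0.842 × 0.6131]² / 0.0081 = 444.6, so 445 per group, 890 in total.

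**The case against.** The strongest reply is that this is loose drafting and that the intent can be recovered. V.12 itself derives 734 shortly before the sentence in question, so the conflict over 367 lies partly inside that section. The sentence speaks of completed enrolment and uses the exact per-group number, so a slip is the natural explanation. On the outcomes, the first item in V.12 agrees with V.3 and is the only one sized, both items count the same event, and no passage says that success on either is enough. The link from outcomes to tests is also partly inferred. The chi-square sentence covers categorical variables in general, and the survival sentence concerns time to delirium; no test of a rate per patient-day is named.

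Most of this stands, and it limits the size of the point. It does not remove it. A slip would explain the 367 but not the second primary outcome, for which V.12 gives no order and no alpha rule. No other section says which reading of 367 is meant. The only mention of interim results, in V.11, is an unanswered form prompt for multi-site studies.

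A reader might go further and infer that an unadjusted interim analysis is planned, with an error rate of 8.3%, or about 9.8-12.0% if either outcome also counted at either look. The documents do not support that. It requires a real look, made by arm, able to support a claim or an early stop, and for the higher figures an either-outcome rule as well. No passage states any of these.

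**Conclusion.** The point holds as a should-fix inconsistency. The part that stands on every reading of 367 is the missing rule for two primary outcomes. Its effect is nil if per admission alone decides (5%). It is modest if either outcome were accepted: about 6-7% at the assumed correlations, and 9.75% at the independent extreme. The 367 is most likely a slip for 734 (367 per group), and then power stays at 80% and no error rate changes. The 50.7% power and the 8.3% error rate each belong to a less likely reading that the text leaves open.

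Confidence is high that the text is inconsistent. It does not extend to the inflation figures, which are conditional on rules that the documents do not state. In particular, it cannot be concluded that the trial's false-positive rate exceeds 5% or that the trial is underpowered.

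**What to change.** 1. **Outcome.** In V.12, make delirium per admission the sole primary outcome, in line with V.3 and the sample size, and move the per-patient-day outcome to secondary. Alternatively, keep both in a fixed sequence, testing per patient-day at 5% only after per admission has succeeded. N stays 734 and power stays 80%. The only cost is that per patient-day alone cannot support a primary claim. Splitting alpha would be the expensive route (71.2% power at 734, or 890 subjects).

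2. **Number at analysis.** The sponsor confirms what was meant and, if it is a slip, changes the sentence to 734 subjects (367 per group). This costs nothing.

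3. **Only if a half-way look is really intended.** Either state that it is pooled and blinded with no comparison by arm, which costs no power, or give a pre-specified group-sequential boundary. For example, an O'Brien-Fleming-type boundary would use about p<0.003 at 367 and p<0.049 at 734. Overall power would then go from 80.0% to 79.85% at the same 734. In that case also state that only whether the boundary was crossed is reported, so that the blinding described in VII.5 is kept.
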